## 7.2. Subject Exclusion Criteria

Subjects must not meet any of the following criteria on screening examination to be eligible to participate in the trial:

1. Has received an anti-tumor therapy including investigational drug within 4 weeks prior to trial drug administration
2. Is currently receiving any agent with a known effect on the immune system, unless at dose levels that are not immunosuppressive (eg, inhaled corticosteroids at doses used for the treatment of asthma) (see [Section 8.1.1](#))
3. Has any other serious illnesses or medical conditions such as, but not limited to:
  - a. Any uncontrolled infection
  - b. Uncontrolled cardiac failure classification III or IV (New York Heart Association)
  - c. Myocardial infarction  $\leq$ 6 months prior to enrollment
  - d. Serious or uncontrolled cardiac arrhythmia, unstable angina
  - e. History of or active seizure disorder
  - f. History of or active auto-immune disease (excluding mild conditions, such as vitiligo, type 1 diabetes, psoriasis)
  - g. History of or active interstitial lung disease/pneumonitis requiring treatment with systemic steroids
  - h. Prior organ transplant
4. Baseline pulse oximetry <92% on room air at screening

5. Known history of positive tests for human immunodeficiency virus/acquired immune deficiency syndrome (HIV)/AIDS or hepatitis B
6. Hepatitis C subjects are excluded unless they have had a sustained virologic response to direct-acting antiviral therapy; such subjects must have an undetectable hepatitis C virus RNA at screening
7. Active severe acute respiratory syndrome (SARS)-CoV-2 (excluding subjects who have completed 2 weeks of quarantine and are considered clinically stable per investigator judgement); SARS-CoV-2 antibody test positivity is permitted.
8. Pregnant or lactating females
9. Women of childbearing potential who have a confirmed positive pregnancy test result at Baseline. If the urine test is positive or cannot be confirmed as negative, a serum pregnancy test will be required.
10. Had any other malignancies within the last 3 years (except for adequately treated carcinoma of the cervix, bladder, prostate, basal or squamous cell skin cancer), and in the investigator's judgement, there is no anticipation that the patient would need treatment for the other malignancy in the next 2 years, except for endocrine therapy for early-stage tumors.
11. Known malignant brain lesion(s). Subjects with previously treated brain metastases may be eligible provided they are stable (ie: without evidence of progression by imaging for at least 4 weeks prior to the first dose of ELI-002 7P, and any neurologic symptoms have returned to baseline), and there is no evidence of new or enlarging brain metastases.
12. Pancreatic neuroendocrine tumor or germline BRCA 1/2
13. If a subject has pancreatic cancer:
  - a. Any tumor mutation where specific therapy is approved, and the subject is able to receive the approved therapy (except in cases where the subject cannot receive the approved therapy, such as due to a contraindication)
14. If subject has CRC:
  - a. Prior immunotherapy as part of their adjuvant regimen
  - b. Mismatch repair defective (MSI+)
  - c. Any tumor mutation where specific therapy is approved, and the subject is able to receive the approved therapy
15. If subject has NSCLC:
  - a. Any tumor mutation where specific therapy is approved, and the subject is able to receive the approved therapy
16. If subject has ovarian cancer, BRCA 1/2 or other hereditary cancer syndrome

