**Table 12: Schedule of Assessments- Immunization Period**

Assessment	Immunization Period						
	Visit 3	Visit 4	Visit 5	Visit 6	Visit 7	Visit 8	
Day (± days)	Day 57 Baseline (prior to dosing)	Day 57 (dosing) (±3 days)	Day 64 (±3 days)	Day 71 (±3 days)	Day 78 (±3 days)	Day 92 (±3 days)	Day 106 (±3 days)
Dose #	-	Dose 1	Dose 2	Dose 3	Dose 4	Dose 5	Dose 6
Patient reported outcomes	X 		X 	X 	X 	X 	X 
Review medical history	X 						
Review cancer history/prior treatments	X						
Physical Exam	X 		X 	X 	X 	X 	X 
Vital signs	X	X	X	X	X	X	X
Weight	X		X	X	X	X	X
ECG	X						
ECOG	X		X	X	X	X	X
Concomitant medications	X		X	X	X	X	X
Clinical laboratory (local laboratory)	X 		X 	X 	X 	X 	X 
ctDNA (central laboratory) 	X 				X 		
Whole blood-PBMC collection for immunogenicity testing (central laboratory)				X 		X 	
Serum collection of cytokine assay (local laboratory)	X 		X 	X 	X 	X 	X 
High Resolution HLA typing (central laboratory)	X 						
Trial drug (ELI-002) administration		X 	X 	X 	X 	X 	X 
Adverse events	X 	X 	X 	X 	X 	X 	X 
Reactogenicity diary 		X	X	X	X	X	X

CA=carbohydrate antigen; CBC=complete blood count; CEA=carcinoembryonic antigen; CRC=colorectal cancer; CRS=cytokine release syndrome; CT=computed tomography; ctDNA=circulating tumor deoxyribonucleic acid; ECG=electrocardiogram; ECOG=Eastern Cooperative Oncology Group; HLA=human leukocyte antigen; IFN $\gamma$ =interferon gamma; IL=interleukin; mKRAS=mutant Kirsten rat sarcoma; mNRAS=mutant neuroblastoma ras viral oncogene homolog; MRD=minimal residual disease; PBMC=peripheral blood mononuclear cell; PDAC=pancreatic ductal adenocarcinoma; PE=physical examination; TNF $\alpha$ =tumor necrosis factor alpha

1. The patient reported outcomes (PROs) will include the general QLQ-C30, as well as a specific PRO for the subject's tumor type (see [Section 11.3](#)). PROs must be completed prior to other study visit procedures.

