Adjuvant, eg, capecitabine, 5-FU oxaliplatin, capecitabine oxaliplatin, gemcitabine capecitabine, gemcitabine cisplatin, 5-FU cisplatin, capecitabine cisplatin, 5-FU, gemcitabine (gallbladder and intrahepatic CCA only)

Chemoradiation, eg, XRT with 5-FU, XRT with capecitabine

10. Screening CT is negative for recurrent disease

11. Laboratory values must be:

- a. Absolute neutrophil count  $\geq 1.5 \times 10^9/L$
- b. Platelets  $\geq 100 \times 10^9/L$
- c. Hemoglobin  $\geq 9$  g/dL
- d. Total bilirubin  $\leq 1.5 \times$  ULN, unless subject has documented Gilbert's syndrome
- e. Aspartate aminotransferase (AST) or alanine aminotransferase (ALT)  $\leq 2.5 \times$  ULN
- f. Serum creatinine  $< 1.5$  mg/dL (or if serum creatinine is  $\geq 1.5$  mg/dL, the creatinine clearance calculated by Cockcroft-Gault formula must be  $\geq 60$  mL/min)
- g. Albumin  $\geq 2.5$  g/dL
- h. IL-6  $< 500$  pg/mL

12. Eastern Cooperative Oncology Group (ECOG) performance status of 0 or 1

13. Subjects have recovered from prior surgery, chemotherapy, or radiation without any ongoing medical/surgical issues (excluding resolved, low grade or chronic stable findings such as neuropathy, impaired hearing, or reproductive changes)

14. Women of childbearing potential and men with a female partner of childbearing potential must be willing to use effective methods of contraception during trial participation and for 30 days after the last dose of trial drug to prevent pregnancy as follows:
  - a. Women: willing to use contraceptives with a failure rate <1% per year when used consistently and correctly, eg, combined oral contraceptives, barrier methods, approved contraceptive implant, long- term injectable contraception, or intrauterine device, sexual abstinence, or a vasectomized partner  
  
Definitions that meet the criteria to not be considered of childbearing potential:
    - Women >2 years postmenopausal (defined as 1 year or longer since last menstrual period) AND >55 years of age
    - Postmenopausal women (as defined above) and <55 years of age with a negative pregnancy test within 24 hours of first dose
    - Women who were surgically sterilized at least 3 months prior to enrollment
  - b. Men: willing to use an acceptable method of birth control, eg, condom with spermicide. In addition, men must refrain from donating sperm.
15. Able to provide written (signed) informed consent to participate in the trial prior to any trial specific screening procedures

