#### 10.1.1. Rescreening

Subjects are allowed to rescreen for the ELI-002-001 trial. No screening procedures, other than what may need to be repeated due to screen failure, will need to be repeated as long as the screening CT/MRI scan was performed  $\leq 90$  days from the time of the anticipated first dose of trial drug. If the CT/MRI scan was performed  $>90$  days from the anticipated first dose, then it will need to be repeated and reviewed, to ensure that the patient is negative for recurrent disease, per the protocol inclusion criteria.

Other screening evaluations can be repeated as deemed appropriate and necessary by the investigator.

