## 10.2. Immunization Period

During the Immunization Period, subjects will receive 4 weekly SC injections (Weeks 1 to 4) followed by 2 injections at Week 6 and Week 8 (Table 12). If the subject has fever  $\geq 38.0^{\circ}\text{C}$  and/or elevated IL-6  $\geq 500$  pg/mL, proceed with the visit but omit study treatment administration; if fever abates and cytokines diminish to  $< 500$  pg/mL, the subject may proceed with the next scheduled dose after approval from the medical monitor). In addition, if a subject exhibits IFN $\gamma$   $\geq 1000$  pg/mL, the Elicio medical monitor should be contacted for consultation.

All laboratory samples should be taken prior to dosing on any study visit that has dosing.

At **Visit 3 (Baseline, Day 57) prior to trial drug administration**, the following visit procedures will include:

- Administer the EORTC QLQ-C30 and the tumor type-specific PRO (see Section 11.3).
- Record any change in medical history since the previous visit. Subjects must have recovered from surgery without any ongoing medical/surgical issues.
- Record any change in cancer history since the previous visit.
- Perform a physical examination which will be based on institution standard of care (see Section 12.1.3). In addition, a neurological examination for baseline assessment of ICANS/ICE will be performed.
- Record vital signs (blood pressure, pulse rate, body temperature, and respiratory rate).
- Record weight.
- Perform a 12-lead ECG (to be reviewed by a cardiologist or clinical investigator according to institutional guidelines and practice).
- Confirm ECOG Scale of Performance Status is 0 or 1.
- Record any change in concomitant medications since the previous visit.
- Collect a blood sample for clinical laboratory assessments, including the cytokine panel (local laboratory; see Section 11.1 and Section 12.1.6). Note: cytokine testing should be performed within 7 days prior to dosing.
- Collect a blood sample for ctDNA (to be performed at a central laboratory).
- Collect a blood sample for high resolution HLA typing (central laboratory).
- Record any pre-treatment SAEs that have occurred since the previous visit.

**Dose 1:** The first dose must be administered at the clinical site. Subjects must be observed by study staff for at least 1-hour postdose for observation and must stay within an hour of the clinic for  $\geq 24$  hours in order to monitor for potential AEs such as CRS.

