#### **12.1.6.6. Pregnancy Screen**

A urine pregnancy test will be performed according to the Schedule of Assessments ([Table 11](#)) for women of childbearing potential. Postmenopausal women must have been amenorrhoeic for at least 12 months to be considered of non-childbearing potential. Childbearing status for all women will be recorded in the source documents and in the eCRF.

A positive pregnancy test will exclude the subject from participation in the trial. Any clinically abnormal or inconclusive test will be repeated.

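### The only scheduled pregnancy test falls 23 to 39 days before first dose and does not match the time points that exclusion 9 and inclusion 14 rely on

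*Protocol*

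**What the plan says.** Three parts of the protocol bear on when pregnancy is ruled out.

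- **Exclusion 9 (Section 7.2)** applies to "Women of childbearing potential who have a confirmed positive pregnancy test result at Baseline". The visit that carries that label in Section 10.2 is "Visit 3 (Baseline, Day 57) prior to trial drug administration". Table 12 does the same, with a Baseline column before dosing and the dose itself at "Day 57 (dosing) (±3 days").
- **Inclusion 14 (Section 7.1)** lists the women who are not considered of childbearing potential. One category is "Postmenopausal women (as defined above) and <55 years of age with a negative pregnancy test within 24 hours of first dose".
- **The schedule** has one pregnancy test. Table 11 marks a urine test at Visit 2 (Day 26 ±5), and Section 10.1 limits it to women of childbearing potential. Section 12.1.6.6 says "A urine pregnancy test will be performed according to the Schedule of Assessments" and refers to Table 11 only.

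On rescreening, Section 10.1.1 says "No screening procedures, other than what may need to be repeated due to screen failure, will need to be repeated as long as" the scan is recent enough. The investigator may repeat other evaluations but does not have to.

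SAP Tables 2 and 3 carry the same arrangement: a test at Visit 2 and none at Visit 3.

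**The concern.** The eligibility criteria and the schedule do not point to the same moment. If Baseline in exclusion 9 is the visit that the protocol labels Baseline, the test result it depends on is never scheduled. The 24-hour condition in inclusion 14 has no scheduled visit under any reading. The Visit 2 test is also not scheduled for women whom a site has already classed as not of childbearing potential.

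This is a first-in-human trial of an immunostimulatory product. A site can follow every table exactly and give the first dose to a woman who became pregnant after Visit 2, with no scheduled test in between that would have shown it. A site that follows Sections 7.1 and 7.2 instead has to add a test for which the schedule provides no visit.

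**Working it through.** No sample size or power figure is involved. The check is a comparison of sections and a subtraction of visit days.

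**Inputs**
- Visit 2, the scheduled urine test: Day 26 ±5 (Table 11, Section 10.1), so Day 26 − 5 = 21 to Day 26 + 5 = 31.
- First dose, Visit 3: Day 57 ±3 (Table 12), so Day 57 − 3 = 54 to Day 57 + 3 = 60.

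**Interval from test to first dose**
- Nominal: 57 − 26 = 31 days.
- Shortest within the windows: 54 − 31 = 23 days.
- Longest within the windows: 60 − 21 = 39 days.

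**Against inclusion 14.** The condition allows 24 hours, or 1 day. The shortest interval is 23 days, so the Visit 2 test misses it by at least 23 − 1 = 22 days. No combination of visit windows closes that gap.

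**Against exclusion 9.** There are two possible readings of Baseline.
- *Baseline is Visit 3.* This is how Table 12 and Section 10.2 use the term. The itemised Visit 3 procedures in Section 10.2 contain no pregnancy test. The clinical laboratory row of Table 12 does not include one either: its footnote covers hematology, chemistry, coagulation and cytokines. The result is not scheduled.
- *Baseline is screening.* Section 7.2 opens by applying its criteria at the screening examination, and exclusion 4 uses Baseline for a screening measurement. The Visit 2 test then satisfies the wording, and the 23 to 39 days before dosing remain without a scheduled test.

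**Other schedules.** Tables 13 to 16 contain no pregnancy test.

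**Rescreening.** Section 10.1.1 requires repetition of what caused the screen failure, and of the scan if it is too old. A pregnancy test that was not the cause of failure need not be repeated. The section sets no maximum age for it and does not say how the 56-day screening window in the Table 11 footnote applies to a rescreened subject. The upper end of the interval is therefore not defined for these subjects.

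**The case against.** The strongest reply is that exclusion 9 and the schedule agree. Section 7.2 speaks of the screening examination, exclusion 4 shows that Baseline can mean screening there, and Section 12.1.6.6 is headed as a pregnancy screen and refers to the screening table. This stands as a possible reading, so the defect in exclusion 9 is ambiguity and not a proven contradiction. It does not help inclusion 14, whose 24-hour condition no screening visit can meet.

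There are also safeguards. Exclusion 8 bars "Pregnant or lactating females", inclusion 14 requires effective contraception, unscheduled re-tests are allowed, an inconclusive test is repeated, and Section 12.6 requires pregnancies to be reported. These lower the risk, but none of them schedules a test between Visit 2 and first dose.

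A reader might infer more than the documents support:
- *That exclusion 8 cannot be applied at its time point.* It names no time point.
- *That every woman needs a test within 24 hours of dosing.* The condition only decides whether a postmenopausal woman under 55 is classed as not of childbearing potential. Without it she falls back to childbearing potential, which is the cautious direction.
- *That the menopause definitions conflict.* Section 12.1.6.6 asks for 12 months without menses. Inclusion 14 contains the same one-year definition and adds conditions to it, so the two can be satisfied together.
- *That a rescreened subject's test may be up to 90 days old.* The 90 days in Section 10.1.1 limit the age of the scan. No limit is given for the pregnancy test.
- *That a test before the booster doses has been omitted.* No section calls for one.

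**Conclusion.** The point holds as a mismatch between eligibility criteria and schedule. The only scheduled pregnancy test comes nominally 31 days before first dose, with a range of 23 to 39 days. It cannot meet the 24-hour condition in inclusion 14. It meets exclusion 9 only if Baseline is read as screening, against the label that Table 12 and Section 10.2 give to Visit 3. On rescreening the interval has no stated limit.

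The figures assume that visits take place within their windows and that no unscheduled test is done. The documents give no number of women affected, so the expected number of exposed pregnancies cannot be estimated. It may be small. The change is worth making because the consequence for a subject and her fetus could be serious and the repair is cheap.

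**What to change.** The sponsor should reconcile exclusion 9, inclusion 14, Tables 11 and 12, and Sections 10.1, 10.1.1, 10.2 and 12.1.6.6, and then bring SAP Tables 2 and 3 into line. Three things need to be settled:

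1. Which visit Baseline means in exclusion 9, stated explicitly.
2. A schedule entry for the pregnancy test at the time point that the eligibility criteria rely on, covering the women to whom inclusion 14 applies its 24-hour condition.
3. The same time point for rescreened subjects, so that the general waiver in Section 10.1.1 does not leave the age of the test open.

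Which time point is right is for the sponsor to decide. The requirement here is only that the sections agree. The cost is one schedule row, matching text and a little site work. Urine and serum pregnancy testing are already in the protocol.

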### **6.7.2. Permanent Stopping Treatment Administration**

If a subject meets any of the following conditions, the subject will be required to discontinue the trial treatment administration but should continue other trial-related procedures as specified for the follow-up period of the study. (See [Section 7.3](#) for more information on procedures for subjects withdrawn from trial treatment.)

1. Evidence of radiographic disease progression
2. Any intolerable AE, at the investigator's discretion

3. During study treatment:
  - Any investigational product use other than ELI-002
  - Other anti-cancer treatment
4. Non-compliance with trial treatments/procedures. If a subject misses  $\geq 2$  trial visits without underlying toxicity, the subject should be re-instructed regarding dosing and follow-up and continue trial participation. If a subject continues to miss trial visits without toxicity and despite re-instruction, they should be discontinued from the trial treatment phase but follow-up data should be collected as possible.
5. The subject requests to be withdrawn from the trial treatment

For subjects whose treatment is discontinued prematurely, the procedures outlined for End of Treatment/Visit 15 (Table 14) will be carried out and, if possible, prior to the initiation of any other anti-cancer treatment. These subjects should then enter the Follow-up Period, where procedures listed in Table 15 and Table 16 will be performed. In the event that a subject will not continue to be evaluated in the Follow-up Period, the End of Study visit (Visit 24) should be scheduled, and all procedures performed.

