
Clearance
	
Define as the percent change from baseline of the on-study ctDNA, or CA19-9, or CEA that achieved -100%.
 
Notes:
 
 
a. Clearance start will be the date of first clearance.
 
b. Once clearance start date is identified for a biomarker, the same biomarker will be used to determine the clearance end date.
 
c. Results will not be considered if a subject has already started taking subsequent anti-cancer therapy.
 
d. If there is a tie for best response across biomarkers, select ctDNA first.                             
 
▪ For PDAC subjects, select CA19-9 second, CEA third.
 
• For CRC subjects, select CEA second, CA19-9 third.
 
 
 

Reduction
	
Defined as the percent change from baseline of the on-study ctDNA, or CA19-9, or CEA that achieved any decrease (i.e., a negative percent change from baseline).
 
Notes:
 
 
a. Reduction start will be the date of first reduction.
 
b. Once reduction start date is identified for a biomarker, the same biomarker will be used to determine the reduction end date.
 
c. Results will not be considered if a subject has already started taking subsequent anti-cancer therapy.
 
d. If there is a tie for best response across biomarkers, select ctDNA first.                             
 
• For PDAC subjects, select CA19-9 second, CEA third.
 
• For CRC subjects, select CEA second, CA19-9 third.
 
 
 

Duration of Biomarker Clearance/Reduction
	

Clearance Duration
	
This is confirmed after clearance start by an increase above -100% change from baseline followed by a second increase above -100% at least 1 week afterwards.
 
Notes:
 
 
a. The end date will be the date of the first subsequent increase.
 
b. If the increase cannot be confirmed by a second increase, then the potential end date of biomarker clearance will proceed to the next increase and so on.
 
c. Subjects with confirmed clearance duration will not be censored.
 

Reduction Duration
	
This is confirmed after reduction start by an increase above the initial reduction followed by a second increase above the initial reduction at least 1 week afterwards.

**Final Analysis  

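### Exclusion 10 is inverted as written: an unlisted recent second cancer excludes a subject when no treatment is anticipated, and does not exclude under this criterion when treatment is anticipated

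*Protocol*

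**What the plan says.** Protocol Section 7.2 opens with the rule that governs the whole list: "Subjects must not meet any of the following criteria on screening examination to be eligible to participate in the trial". Meeting a criterion therefore makes a subject ineligible.

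Criterion 10 is a single sentence in four pieces:

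- the base condition, "Had any other malignancies within the last 3 years";
- a bracketed exception and the connective after it, "except for adequately treated carcinoma of the cervix, bladder, prostate, basal or squamous cell skin cancer), and in the investigator's judgement";
- the clause on future treatment, "there is no anticipation that the patient would need treatment for the other malignancy in the next 2 years";
- a closing carve-out, "except for endocrine therapy for early-stage tumors".

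Four other places bear on it:

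- Protocol Section 6.7.2, item 3, lists "Other anti-cancer treatment" during study treatment among the reasons for permanently discontinuing ELI-002.
- Protocol Section 8.1.1 bars any other cancer therapy while study drug is being given and makes its use a criterion for permanent stopping.
- SAP Table 8, in the notes to both biomarker clearance and biomarker reduction, says "Results will not be considered if a subject has already started taking subsequent anti-cancer therapy".
- SAP Table 16 has separate RFS rows for subjects who have started subsequent anti-cancer therapy. In the primary RFS analysis these refer back to the last evaluable scan before that therapy began.

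Neither SAP table limits the therapy to treatment of the study tumour.

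**The concern.** An exclusion criterion on second cancers normally keeps out subjects whose other tumour is active enough to need treatment. As punctuated, this one does the opposite for cancers outside the bracket. Its absence-of-treatment clause is joined to the base condition by *and*, so it narrows the excluded group to those who need nothing further.

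Two things are at stake. First, a site that follows the text could turn away a subject with a quiescent second cancer. It would also find nothing in criterion 10 against a subject whose second cancer is about to be treated, the kind of subject for whom the stopping sections and the SAP's subsequent-therapy rules may later apply. Second, a site that sees the slip and corrects it mentally has to guess the intended rule, and more than one guess is reasonable. Eligibility decisions could then differ between sites. So could the identification of major violations for the Per Protocol Set (SAP Section 11.3).

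**Working it through.** No figure is involved, so the check is one of logic. Define:

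- A: another malignancy within 3 years that is not a listed, adequately treated cancer (an *unlisted* cancer);
- B: no treatment for the other malignancy anticipated in the next 2 years, disregarding endocrine therapy for an early-stage tumour.

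The bracket closes before the comma and *and*, so the literal rule is: excluded if A and B.

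Two repairs are plausible:

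- *Alternative*: excluded unless the cancer is listed and adequately treated, **or** no treatment is anticipated.
- *Added requirement*: excluded unless the cancer is listed and adequately treated **and** no treatment is anticipated.

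| Other malignancy in last 3 years | Treatment anticipated | Literal text | Alternative | Added requirement |
|---|---|---|---|---|
| 1. Unlisted | None | Excluded | Not excluded | Excluded |
| 2. Unlisted, early stage | Endocrine only | Excluded | Not excluded | Excluded |
| 3. Unlisted | Other treatment | **Not excluded** | Excluded | Excluded |
| 4. Listed, adequately treated | None | Not excluded | Not excluded | Not excluded |
| 5. Listed, adequately treated | Other treatment | Not excluded | Not excluded | Excluded |

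What follows from the table:

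- Row 3 is wrong under either repair. Together with row 1, it is the inversion.
- Rows 1, 2 and 5 depend on which repair is meant, so correcting the direction alone does not settle the rule.
- Row 2 is internal evidence of a drafting error. The endocrine carve-out reads as a permission, yet literally it adds subjects to the excluded group.
- Criteria 6 and 11 of the same list mark their exceptions with explicit words (*unless*; *may be eligible provided*). Criterion 10 does not.

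Against the stopping sections: dosing runs from Day 57 (Protocol Table 12) to Day 217 (Protocol Table 14), which is 217 − 57 = 160 days. Criterion 10 looks ahead 2 years, or 2 × 365 = 730 days. Sections 6.7.2 item 3 and 8.1.1 therefore bear on a row 3 subject only if the other therapy falls within about 160/730 = 22% of that horizon. SAP Tables 8 and 16 can apply later as well.

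Weight of one subject: cohorts hold 3 to 6, so one subject is 1/6 = 17% to 1/3 = 33% of a cohort's biomarker or RFS summary. This is not an estimate of how often it happens; the documents give no count of subjects with a second malignancy.

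**The case against.** The strongest reply is that the intent is visible in the sentence, that investigators will read it sensibly, and that other criteria stand behind it. Much of this is fair. The direction of the slip is easy to guess, and nothing in the documents shows that any site applied the literal logic.

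A row 3 subject is also only *not excluded by criterion 10*. A reader might infer that such a subject is eligible outright, but the documents do not say so. Exclusion 1 removes anyone within its window: "Has received an anti-tumor therapy including investigational drug within 4 weeks prior to trial drug administration". Exclusion 3 is open-ended about serious illness, and inclusion 13 requires recovery from earlier cancer treatment. These narrow the gap without closing it: exclusion 1 looks back only 4 weeks, exclusion 3 names no malignancy and leaves the decision to discretion, and inclusion 13 concerns past treatment.

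Two further inferences are tempting and not supported:

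- *That trial treatment will be stopped in subjects so admitted.* The stopping sections apply only during dosing. Therapy for the other cancer that is needed later would not trigger them.
- *That the inversion lets a second tumour supply the qualifying CEA, CA19-9 or CA-125 value.* Inclusion 4 rules out only non-cancer causes of a raised marker, and the bracket in criterion 10 admits some other treated cancers under any reading. That gap belongs to inclusion 4. On the tumour-informed ctDNA route it is further limited, because the assay tracks 16 variants from the subject's own sequenced tumour (Protocol Section 6.1.5.1.1).

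The reply about intent fails on one point. Guessing the direction does not tell a site which repair is meant, and rows 1, 2 and 5 turn on that.

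**Conclusion.** The point stands as an error in an operative eligibility rule. As written, criterion 10 excludes a subject with an unlisted recent malignancy when no treatment, or only endocrine therapy for an early-stage tumour, is anticipated; it does not exclude that subject when other treatment is anticipated. No other section of the protocol or SAP restates or corrects it. It is at odds with Protocol Sections 6.7.2 and 8.1.1 and with the subsequent-therapy rules in SAP Tables 8 and 16, and it invites inconsistent application between sites.

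The size is limited. The effect falls on cancers outside the bracket, in an unknown and possibly zero number of subjects. It touches biomarker, RFS and OS summaries that the SAP treats descriptively. Sample size and the DLT rules are unaffected, and no effect on the primary safety conclusion is shown. The conclusion assumes that the punctuation is what sites saw and that the opening sentence of Section 7.2 governs the list. It should be corrected because the correction is cheap, not because harm to the results has been demonstrated.

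**What to change.** 1. Reword criterion 10 so that the clause on anticipated treatment works as an exception, introduced by *unless*. The sponsor must state whether it is an alternative to the listed, adequately treated cancers (admitting rows 1 and 2, and leaving row 5 admitted) or an added requirement for them (excluding rows 1, 2 and 5). These are materially different populations, and the documents do not show which was meant.
2. Reconcile the endocrine carve-out with Protocol Sections 6.7.2 and 8.1.1. If it is a permission, the criterion foresees a cancer therapy that those sections, as worded, do not exempt. The sponsor should say how the three fit together.
3. The Protocol Synopsis gives 2Q2023 for the last subject enrolled, so if that held, rewording alone would change no enrolment. Check the screening log and medical histories for any enrolled or screen-failed subject with another malignancy in the previous 3 years, and record which reading was applied. Report any such subject in the study report and classify the deviation for the Per Protocol Set against the clarified rule. Carry the corrected wording into any later protocol that reuses this list.

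The cost is one sentence in the protocol, a cross-check of two sections, and a review of records for a trial planned at about 18 subjects plus its screen failures. No new data or patients are needed.
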